### **3.3. Benefit/Risk Assessment**

Based on LY3074828 nonclinical and preliminary clinical data, there are no anticipated risks requiring monitoring beyond those for a typical humanized monoclonal antibody in human studies. As with other immunomodulatory therapies, LY3074828 may increase the risk of developing an infection or may exacerbate an existing serious infection. These may include opportunistic infections and reactivation of latent infections, such as tuberculosis (TB) and hepatitis B. Subjects will therefore be screened for hepatitis B/C, human immunodeficiency virus (HIV), and TB.

Treatment-emergent ADAs have been observed in 2 of the 11 healthy subjects that have been administered SC doses of LY3074828; however, titers were  $\leq 1:160$ . No clinically significant safety or tolerability concerns have been identified in patients or subjects to date for LY3074828 up to the highest dose given (single 1200-mg IV doses).

Healthy subjects are not expected to derive any benefit from participating in studies of LY3074828.

Possible device-based risks include local effects such as pain at the injection site from either the needle or the solution entry into the SC tissue, swelling, erythema, bleeding, and bruising. Systemic effects may include sweating, feeling faint, or fever, as a sign of infection. These risks are mitigated by sterile filling of the semi-finished syringes (SFSs), assembly of devices that meet regulatory standards, training of investigative site staff and subjects on proper injection techniques, and monitoring of the subjects to ensure injections are performed properly.

More information about the known and expected benefits, risks, SAEs, and reasonably anticipated AEs of LY3074828 are to be found in the Investigator's Brochure (IB).

More information about the known and expected benefits, risks, SAEs, and reasonably anticipated AEs of the AI is found in the device IB.

## 4. Objectives and Endpoints

Table AMAQ.1 shows the objectives and endpoints of the study.

**Table AMAQ.1. Objectives and Endpoints**

Objectives	Endpoints
Primary	
Part A 
 
To evaluate the PK of LY3074828 solution formulation after administration of 250-mg doses using 2 x 1-mL and 1 x 2-mL PFS injections in healthy subjects.
 
To assess the safety and tolerability of, and pain associated with, LY3074828 PFS administrations in healthy subjects.
 
	Part A 
 
The primary PK endpoints will be the <math>C_{max}</math>, <math>AUC(0-t_{last})</math>, and <math>AUC(0-\infty)</math> of LY3074828.
 
Incidence of TEAEs.
 
SF-MPQ, including VAS pain score.
 

Part B 
 
To compare the safety and tolerability of, and pain associated with, LY3074828 solution formulation after administration of 125- and 250-mg doses using 1-mL AI and 2-mL AI SC injections with different injection speeds (slow and fast) in healthy subjects.
 
	Part B 
 
Incidence of TEAEs.
 
SF-MPQ, including VAS pain score.
 

Abbreviations: AI = autoinjector;  $AUC(0-\infty)$  = area under the concentration versus time curve from time zero to infinity;  $AUC(0-t_{last})$  = area under the concentration versus time curve from time zero to time  $t$ , where  $t$  is the last sample with a measurable concentration;  $C_{max}$  = maximum observed drug concentration; PFS = pre-filled syringe; PK = pharmacokinetic; SC = subcutaneous; SF-MPQ = Short Form McGill Pain Questionnaire; TEAE = treatment-emergent adverse event; VAS = visual analog scale.

## 5. Study Design

### 5.1. Overall Design

Study I6T-MC-AMAQ (AMAQ) is a single-center, randomized, parallel-treatment, open-label, Phase 1 single-dose study of LY3074828 solution formulation in healthy subjects. In Part A, PK, safety and tolerability of, and pain associated with, SC doses administered using 1- and 2-mL PFS injections will be evaluated. In Part B, safety and tolerability of, and pain associated with, single AI injections of 1- and 2-mL that will be administered with 2 different injection speeds will be evaluated.

**Screening Period ( $\leq 28$  days):** Subjects will be evaluated for study eligibility  $\leq 28$  days prior to enrollment.

**Residential Period (2 days [Part A] or 3 days [Part B]):** A total of approximately 72 subjects (approximately 36 subjects per study Parts A and B) who fulfill the eligibility criteria will be randomized to 1 of 2 dosing regimen arms within their assigned study part, with 18 subjects randomized to each arm in order to ensure completion of 16 subjects in each:

#### Part A

- Reference: 250 mg LY3074828 solution formulation, 2 x 1-mL 125-mg/mL PFS injections using an investigational PFS targeting 5- to 10-second injection time for each injection
- Test 1: 250 mg LY3074828 solution formulation, 1 x 2-mL 125-mg/mL PFS injection using an investigational PFS targeting 5- to 15-second injection time

#### Part B

- Tests 2 and 3: 250 mg LY3074828 solution formulation, 1 x 2-mL 125-mg/mL AI slow injection (Test 2; targeting approximately 13-second injection time) and fast injection (Test 3; targeting approximately 5-second injection time) using an investigational 2-mL AI
- Tests 4 and 5: 125 mg LY3074828 solution formulation, 1 x 1-mL 125 mg/mL AI slow injection (Test 4; targeting approximately 7-second injection time) and fast injection (Test 5; targeting approximately 4.5-second injection time) using an investigational 1-mL AI

For Part A, subjects will report to the clinical research unit (CRU) on Day -1 and will remain at the CRU until the scheduled procedures have been completed on Day 2. After randomization to either a 2 x 1-mL or a 1 x 2-mL 125-mg/mL PFS dose regimen, study drug will be administered by investigative site staff by SC injection in the abdomen in the morning of Day 1 after an overnight fast.

For Part B, subjects will report to the CRU on Day -1 and will remain at the CRU until the scheduled procedures have been completed on Day 3. Subjects will be randomized to receive, on Days 1 and 2, either a 1 x 1-mL or a 1 x 2-mL 125-mg/mL AI dose regimen. The allocated

AI dose regimen will be self-administered by slow and fast SC injection(s) on consecutive days (sequence randomized) in the abdomen after an overnight fast.

**Outpatient Follow-up Period (12 weeks):** The follow-up period will include outpatient visits for a total of 12 weeks (Days 4, 8, 11, 15, 22, 29, 43, 57, 71, and 85 for Part A; Days 15, 43, and 86 for Part B) following dose administration on Day 1 to assess the PK, safety, and tolerability of, and pain associated with, LY3074828 PFS administrations for Part A, and to assess the safety and tolerability of, and pain associated with, LY3074828 investigational AI administrations for Part B.

Safety and tolerability will be explored by clinical laboratory tests, vital sign measurements, 12-lead ECGs, recording of AEs and product complaints, physical examinations/medical assessments, immunogenicity, and injection-site assessments. Pain assessments will be made using the Short Form McGill Pain Questionnaire (SF-MPQ), which includes a subject-assessed injection-site pain visual analog scale (VAS).

## 5.2. Number of Participants

A total of approximately 72 subjects (approximately 36 subjects per study Parts A and B) who fulfill the eligibility criteria will be randomized to 1 of 2 dosing regimen arms within their assigned study part, with 18 subjects randomized to each arm in order to ensure completion of 16 subjects in each. A subject's study participation is considered as complete if he/she receives the study drug as per the protocol requirements and completes all activities up to and including at least Day 57 for Part A or up to and including at least Day 15 for Part B. A maximum of 4 subjects per arm per study part may be replaced if multiple subjects do not complete the study.

## 5.3. End of Study Definition

End of the study is the date of the last visit or last scheduled procedure shown in the Schedule of Activities (Section 2) for the last subject.

## 5.4. Scientific Rationale for Study Design

Conducting the study in healthy subjects mitigates the potential confounding effects of the disease state and concomitant medications in patients. Healthy subjects are frequently used in the assessment of bioavailability of both small and large molecules.

For Part A, single doses of LY3074828 and the PK sampling time points have been selected to generate PK profiles sufficient to fulfill the study objectives. As the primary endpoints for Part A of this study are PK-related and are not subject to bias, it is not considered necessary for this study to be blinded. Subjects and site staff will be aware of the administration route and treatment.

For Part B, only an evaluation of safety and tolerability of, and pain associated with, the investigational AI administrations is intended. Pharmacokinetic samples are collected only in conjunction with immunogenicity samples to provide concentrations of LY3074828 to aid in the interpretation of ADA data if needed.

For Part A, a parallel-group design was chosen because a crossover design is impractical for compounds that have long half-lives, such as monoclonal antibodies. Additionally, a crossover study design could confound PK data if subjects develop neutralizing ADAs.

For Part B, a crossover design was chosen as PK analysis is not an endpoint and a relatively short time between injections will allow a more accurate comparison of injection-site pain by subjects

Monoclonal antibody therapy has been associated with hypersensitivity reactions, including injection-site reactions. Follow-up details on injection-site reactions will be collected by the investigative site regarding the severity, duration, type, and timing of the start of the event in relation to the start of study drug administration in order to further characterize these events.

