## **7.3. Blinding**

This is an open-label study; however, subjects in Part B will not be informed as to whether the AI is fast or slow injection speed.

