#### **9.4.4.6. Injection-site Pain**

##### **9.4.4.6.1. Short Form McGill Pain Questionnaire**

Acute pain from SC injection will be assessed using the 15-item short form of the SF-MPQ (Melzack 1987) modified to meet the purpose of the study at times specified in the Schedule of Activities (Section 2).

As part of the SF-MPQ, pain measurements will be quantified using the 100-mm validated VAS for all subjects, whether or not they report injection pain. The VAS is a well-validated tool (Williamson and Hoggart 2005) to assess injection-site pain; it is presented as a 100-mm line

anchored by verbal descriptors, usually “no pain” and “worst possible pain.” The subject will be asked to rate any pain on a scale of 0 to 100 mm on the line immediately (approximately within 5 minutes) following the start of the injection and at the time points listed in the Schedule of Activities (Section 2).

For 1-mL PFS, assessments are to be completed on the first of the 2 injections only.

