#### **9.4.8 Pain Assessment**

Pain will be assessed by the SF-MPQ and will be quantified using the 100-mm validated VAS where 0 mm represents "no pain" and 100 mm represents "worst possible pain". Assessments will be performed at 0, 15, 30, 60, 120, and 240 minutes post injection; however, the primary endpoint will be the 0-hour assessment.

The data will be summarized by treatment and timepoint and listed for individual subjects. Individual profiles will be presented over time. Furthermore, scatter plots of the 0, 15 and 30 minutes post injection pain scores will be presented by treatment.

In Part A, a linear fixed-effects model will be used to analyze the 0-hour (post-injection) pain VAS score and SF-MPQ total score. The model will include treatment (Reference or Test 1) as a fixed effect. The least squares means and differences in least squares means (between Test 1 and Reference) will be presented along with the corresponding 90% CI. Similar SAS code to the PK statistical analysis will be used.

The distribution of the data will be explored prior to analysis to determine whether data transformation is required. It is possible that the pain scores will be 0 so if the distribution of the data implies that a log-transformation is required then the score may be updated to  $\log(VAS+1)$  to allow for the inclusion of the 0 values in the analysis.

A similar model will be used to analyze the 0-hour (post-injection) pain VAS score and SF-MPQ total score in Part B.

The following comparisons will be performed in Part B:

- Test 2 versus Test 3 (slow versus fast injection for 2-mL AI)
- Test 4 versus Test 5 (slow versus fast injection for 1-mL AI)

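### The no-bias reason for leaving Part A unblinded holds only for the PK endpoints; subject-rated pain and TEAEs are Part A primary endpoints too and are open to expectation bias

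*Protocol*

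**What the plan says.** Protocol Section 5.4 explains the lack of blinding in Part A: "As the primary endpoints for Part A of this study are PK-related and are not subject to bias". It then adds: "Subjects and site staff will be aware of the administration route and treatment". No other reason is offered for Part A.

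Table AMAQ.1 and the synopsis set two primary objectives for Part A. One concerns PK. The other reads "To assess the safety and tolerability of, and pain associated with, LY3074828 PFS administrations in healthy subjects". Beside Cmax and the two AUCs, the Part A primary endpoints include "Incidence of TEAEs" and "SF-MPQ, including VAS pain score".

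Pain is rated by the subject (Protocol Section 9.4.4.6.1): "The subject will be asked to rate any pain on a scale of 0 to 100 mm on the line immediately", within about 5 minutes of the start of injection. In the Reference arm only the first of the two 1-mL injections is rated. Protocol Section 10.3.1.2.1 and SAP Section 9.4.8 name the 0-hour assessment as the primary pain endpoint. The SAP will present "differences in least squares means (between Test 1 and Reference"), with a 90% CI.

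Protocol Section 7.3 calls the study open-label but makes one exception: "subjects in Part B will not be informed as to whether the AI is fast or slow injection speed". It states no comparable step for Part A.

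**The concern.** The reason given for open-label treatment has to cover every endpoint it is used for. Here it describes only part of the Part A primary set. A serum concentration does not depend on what the subject expects. A mark on a 100-mm pain line can. Whether an adverse event is reported, and whether it is judged related, can also depend on knowing the treatment.

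Part A is a parallel-group comparison in which each subject rates one regimen. If subjects who know they are getting one 2-mL injection rate pain differently from subjects who know they are getting two 1-mL injections, the planned contrast cannot separate that from a true difference. The 90% CI reflects sampling error only. At stake is how far the Part A pain and TEAE comparisons can be read as effects of the presentation. The PK bridge between the two syringes is not at stake.

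**Working it through.** This is a question of consistency, and the plan gives no figure to reproduce.

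**Step 1: does the premise match the endpoint list?**

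| Part A primary endpoint (Table AMAQ.1) | Who or what produces the value | Does the Section 5.4 reason apply? |
|---|---|---|
| Cmax, AUC(0-tlast), AUC(0-∞) | Validated immunoassay (Protocol 9.5.1) | Yes |
| TEAE incidence | Reported by the subject; relatedness judged by the investigator (Protocol 9.2) | No |
| SF-MPQ with VAS | Marked by the subject (Protocol 9.4.4.6.1) | No |

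The premise covers one of the three groups.

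**Step 2: is a between-arm comparison of an affected endpoint planned?** Yes. Protocol Section 10.3.1.2.1 and SAP Section 9.4.8 model 0-hour VAS and SF-MPQ total score with treatment as the fixed effect, and present Test 1 minus Reference with a 90% CI.

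**Step 3: is partial concealment compatible with this design?** Part B already withholds injection speed from the subject in a study labelled open-label. In Part A, when the rated injection has just been given, a subject in either arm has had one staff-given injection in the abdomen: the single 2-mL or the first 1-mL. Up to the 0-hour rating the number of injections need not reveal the arm. Three things could:
- Quadrant choice. Section 7.1 lets staff or the subject choose the side for a single injection, but two injections use both lower quadrants.
- Skin preparation and site marking (Section 9.4.4.2), if two sites are prepared in one arm and one in the other.
- The second Reference injection, if it comes before the rating is finished. The documents state no interval between the two injections.

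**Step 4: how sensitive is the contrast?** The documents give no SD for VAS and no estimate of expectation bias, so this uses SD units and an assumed range of bias. Other assumptions are normal data, equal SDs and no true difference. The 0-hour rating is on Day 1 and the safety population is everyone dosed, so about 18 per arm is the relevant number, rather than the 16 per arm planned to complete.

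- Half-width of the 90% CI = t(0.95, 2n−2) × √(2/n) SD.
- n = 18: 1.691 × √(2/18) = 1.691 × 0.333 = 0.56 SD.
- n = 16: 1.697 × √(2/16) = 1.697 × 0.354 = 0.60 SD.

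The chance that the 90% CI excludes zero comes from the noncentral t distribution with 2n−2 degrees of freedom and noncentrality b/√(2/n), where b is the assumed bias in SD:

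| Assumed bias b (SD) | n = 18 per arm | n = 16 per arm |
|---|---|---|
| 0 | 10% | 10% |
| 0.1 | 11% | 11% |
| 0.2 | 16% | 15% |
| 0.3 | 23% | 21% |
| 0.5 | 43% | 40% |

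The table shows sensitivity only. It does not estimate the bias in this trial.

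**The case against.** The strongest reply is that little depends on Part A pain. The study declares itself open-label. The Part A objective is to assess pain, whereas Part B is to compare it. No margin, power or decision rule is set for pain, and the sample size rests on PK precision. SAP Section 9.4.13 says no inferential safety analyses are planned. All of this is fair and limits the weight of the point. It does not remove it, because SAP Section 9.4.8 still specifies a between-arm difference with a 90% CI on an endpoint called primary.

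A second reply is that the Part B parallel is loose. Speed is a property inside the autoinjector, while one 2-mL syringe against two 1-mL injections is visible. That stands in part. A reader might infer that Part A could and should have been fully blinded. The documents do not support that, since the second injection discloses the arm. What they support is concealment up to the 0-hour rating, and this needs practical steps beyond withholding a word.

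Third, masking the 0-hour rating does nothing for TEAEs collected over 12 weeks. That stands, and those comparisons can only be labelled.

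Fourth, the second Reference injection would have to wait for the AE questioning that precedes the questionnaire (Protocol Section 9.2.1.4), and then for the 15-item form and VAS. This too stands. The plan is silent on the interval, so the sponsor must confirm feasibility.

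**Conclusion.** The point holds. The Section 5.4 premise is correct for PK and wrong as a description of the Part A primary endpoints as a whole. The Part A pain and TEAE comparisons are therefore exposed to expectation bias that the plan does not acknowledge.

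Its size and direction are unknown. A reader might infer a definite shift in VAS millimetres, or a shift against the 2-mL syringe in particular. The documents support neither: they give no VAS variability, and subjects could expect either the larger volume or the two needles to be worse, or have no expectation. Nor do they support reading the point as a threat to the PK comparison.

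This should be corrected, but it is not fatal to the trial. The inconsistency rests on the documents' own text and needs no assumption. The value of concealing the regimen rests on two: that the rating can be finished before the second Reference injection, and that preparation of the subject does not reveal the arm.

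**What to change.** 1. **Section 5.4.** Limit the no-bias statement to the PK endpoints. Amend the sentence that subjects will know their treatment, so that it agrees with item 2. State that Part A TEAE comparisons, and pain comparisons after 0 hours, are open-label and will be interpreted as such.

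2. **Section 7.3.** As is already done for speed in Part B, do not tell Part A subjects their regimen, and keep the syringe out of their view, until the 0-hour SF-MPQ and VAS for the single rated injection are complete. Have staff choose the quadrant, and make skin preparation and site marking identical in both arms. Sections 7.1 and 9.4.4.2 need matching wording.

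3. **Feasibility.** The sponsor should confirm that the 0-hour rating and the second Reference injection can be sequenced this way. If they cannot, label the 0-hour pain contrast open-label and descriptive as well, in both the protocol and SAP Section 9.4.8.

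Dose and volume per regimen do not change. The cost is a few sentences of protocol text and a site instruction, with no extra staff. It does add steps at the bedside and a constraint on the order of rating and second injection. Concealment is partial, because injection time may hint at volume, and it does not extend to TEAEs. Item 1 is worth making even if item 2 proves unworkable.

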## 5.5. Justification for Dose

CCI

Doses up to 1200 mg were found to be well tolerated when administered by IV infusion in healthy subjects in the single-dose Study AMAD. Subcutaneous bioavailability was approximately 40% in Study AMAA.

## 6. Study Population

Eligibility of subjects for study enrollment will be based on the results of medical history, physical examination, vital signs, clinical laboratory tests, and ECG.

The nature of any conditions present at the time of the physical examination and any preexisting conditions will be documented.

Screening will occur up to 28 days prior to enrollment. Subjects who are not enrolled within 28 days of screening may be subjected to an additional medical assessment and/or clinical measurements to confirm their eligibility.

Prospective approval of protocol deviations to recruitment and enrollment criteria, also known as protocol waivers or exemptions, are not permitted.

### 6.1. Inclusion Criteria

Subjects are eligible for inclusion in the study only if they meet all of the following criteria at screening and/or enrollment:

[1] are overtly healthy male or female subjects, as determined by medical history and physical examination

[1a] male subjects:

- Men, regardless of their fertility status, with non-pregnant women of childbearing potential partners must agree to either remain abstinent (if this is their preferred and usual lifestyle) or use condoms as well as one additional highly effective (less than 1% failure rate) method of contraception (such as combination oral contraceptives, implanted contraceptives, or intrauterine devices) or effective method of contraception (such as diaphragms with spermicide or cervical sponges) for the duration of the study and for 24 weeks following dosing with the study drug
  - Men and their partners may choose to use a double-barrier method of contraception. (Barrier protection methods without concomitant use of a spermicide are not an effective or acceptable method of contraception. Thus, each barrier method must include use of a spermicide. It should be noted, however, that the use of male and female condoms as a double-barrier method is not considered acceptable due to the high failure rate when these barrier methods are combined)
  - Periodic abstinence (e.g., calendar, ovulation, symptothermal, post-ovulation methods), declaration of abstinence just for the duration of a trial, and withdrawal are not acceptable methods of contraception

- Men with pregnant partners should use condoms during intercourse for the duration of the study and for 24 weeks following dosing with the study drug
- Men should refrain from sperm donation for the duration of the study and for 24 weeks following dosing with the study drug
- Men who are in exclusively same-sex relationships (as their preferred and usual lifestyle) are not required to use contraception

[1b] female subjects:

- All female subjects must test negative for pregnancy prior to initiation of treatment as indicated by a negative serum pregnancy test at the screening visit followed by a negative serum pregnancy test within 24 hours prior to exposure
- Women of childbearing potential who are abstinent (if this is complete abstinence, as their preferred and usual lifestyle) or in a same-sex relationship (as part of their preferred and usual lifestyle) must agree to either remain abstinent or stay in a same-sex relationship without sexual relationships with males. Periodic abstinence (e.g., calendar, ovulation, symptothermal, post-ovulation methods), declaration of abstinence just for the duration of a trial, and withdrawal are not acceptable methods of contraception
- Otherwise, women of childbearing potential participating must agree to use one highly effective method (less than 1% failure rate) of contraception, or a combination of 2 effective methods of contraception (for 12 weeks following dosing with the study drug)
  - Either one highly effective method of contraception (such as combination oral contraceptives, implanted contraceptives, or intrauterine device) or a combination of 2 effective methods of contraception (such as male or female condoms with spermicide, diaphragms with spermicide, or cervical sponges) will be used. The subject may choose to use a double-barrier method of contraception. Barrier protection methods without concomitant use of a spermicide are not a reliable or acceptable method. Thus, each barrier method must include use of a spermicide. It should be noted that the use of male and female condoms as a double-barrier method is not considered acceptable due to the high failure rate when these methods are combined

- Women not of childbearing potential may participate and include those who are:
  - infertile due to surgical sterilization (hysterectomy, bilateral oophorectomy, or tubal ligation) or congenital anomaly such as mullerian agenesis; or
  - postmenopausal – defined as either:
    - A woman at least 50 years of age with an intact uterus, not on hormone therapy, who has had either:
      - cessation of menses for at least 1 year; or
      - at least 6 months of spontaneous amenorrhea with a follicle-stimulating hormone >40 mIU/mL; or
    - A woman 55 or older not on hormone therapy, who has had at least 6 months of spontaneous amenorrhea; or
    - A woman at least 55 years of age with a diagnosis of menopause prior to starting hormone-replacement therapy

- [2] are between 18 and 65 years of age, inclusive, at time of screening
- [3] have a body mass index (BMI) of 18.0 to 32.0 kg/m^2, inclusive, at time of screening
- [4] have clinical laboratory test results within normal reference range for the investigative site, or results with acceptable deviations that are judged to be not clinically significant by the investigator
- [5] have venous access sufficient to allow for blood sampling as per the protocol
- [6] are reliable and willing to make themselves available for the duration of the study and are willing to follow study procedures
- [7] are able and willing to give signed informed consent

